5.2 Exclusion Criteria

Yes/No (Response of “yes” = patient ineligible)

5.2.1 Men with known brain or visceral metastases (except regional lymph nodes as defined by section 5.2.5) defined by CT or MRI Imaging of the abdomen or pelvis.

5.2.2 Men who have had LHRH agonist or antagonist hormone therapy in the prior six months.

5.2.3 Men with >5 validated bony metastases.

5.2.4 Men with baseline serum Testosterone <100 ng/dL.

5.2.5 Men with new or progressing lymphadenopathy clearly consistent with prostate metastasis on imaging or proven by pathologic biopsy at any time three months or later following their initial definitive therapy.

5.2.6 Prior or concurrent invasive malignancy (except non-melanomatous skin cancer) or lymphomatous/hematogenous malignancy unless continually disease free for a minimum of 3 years. All patients with in situ carcinoma are eligible for this study (for example, carcinoma in situ of the oral cavity is eligible) except patients with carcinoma of the bladder (including in situ bladder cancer or superficial bladder cancer).

5.2.7 Use of finasteride within 30 days prior to therapy PSA should not be obtained prior to 30 days after stopping finasteride.

5.2.8 Use of dutasteride within 90 days prior to therapy. PSA should not be obtained prior to 90 days after stopping dutasteride.

5.2.9 Previous or concurrent cytotoxic chemotherapy for prostate cancer.

5.2.10 Received systemic therapy with radionuclides (e.g., strontium-89, samarium-153, rhenium-186, or rhenium-188, or Radium Ra-223 dichloride) for the treatment of bony metastases.

5.2.11 Men who will receive radical prostatectomy to the primary site.

5.2.12 Imminent spinal cord compression based on clinical findings and/or magnetic resonance imaging (MRI). Spinal Cord compression will be defined as 360-degree circumferential obliteration of T2 cerebrospinal fluid signal around the spinal cord. Treatment should be completed for spinal cord compression.

5.2.13 Severe, active co-morbidity, defined as follows:

- Unstable angina and/or congestive heart failure requiring hospitalization within the last 6 months
- Transmural myocardial infarction within the last 6 months
- Acute bacterial or fungal infection requiring intravenous antibiotics at the time of registration
- Chronic obstructive pulmonary disease exacerbation or other respiratory illness requiring hospitalization or precluding study therapy at the time of registration
- Hepatic insufficiency resulting in clinical jaundice and/or coagulation defects; note, however, that laboratory tests for liver function and coagulation parameters are not required for entry into this protocol. (Patients on Coumadin or other blood thinning agents are eligible for this study.)
- Acquired Immune Deficiency Syndrome (AIDS) based upon current CDC definition; note, however, that HIV testing is not required for entry into this protocol. The need to exclude patients with AIDS from this protocol is necessary because the treatments involved in this protocol may be significantly immunosuppressive.

5.2.14 Cardiac failure New York Heart Association (NYHA) III or IV
Crohn's disease or ulcerative colitis.

5.2.15 Bone marrow dysplasia.

5.2.16 Fecal incontinence.

5.2.17 Any condition which, in the investigator's opinion, makes the subject unsuitable for trial participation.

I certify that this patient meets all inclusion and exclusion criteria for enrollment onto this study.

Investigator Signature

Date

Time

6 STRATIFICATION

Not Applicable: This study will consist of subjects initially diagnosed with M0 prostate cancer at presentation who have completed definitive treatment to the prostate, seminal vesicles, and regional lymph nodes (if applicable), who then later developed oligometastatic disease.

7 TREATMENT GUIDELINE

7.1 External Beam Radiation Administration Schedule

7.1.1 All external beam radiations oligometastatic sites will commence after cycle one of Radium-223 but prior to cycle two of Radium-223.

7.1.1.1 All lesions seen on bone scan and corroborated by the validating scans will be treated. If there are additional suspicious bone lesions seen on Bone scan, CT, MRI, PET/CT, or treatment-planning simulation scans, but not corroborated by a second scan, they can be targeted at the treating physician's discretion as long as no more than 5 lesions total are targeted with external beam radiation.

7.1.2 External Beam radiation for Oligometastasis

7.1.2.1 Dose Specification

All subjects will receive Stereotactic body or hypofractionated radiation to sites of bone disease seen on imaging studies using any one of the isoequivalent radiation regimens (based on the linear quadratic model with EQD2=60gy and an alpha/beta ration for prostate cancer= 2). EQD2 (equivalent radiobiological dose if converted to 2Gy daily fractions) is being utilized to allow the radiation oncologist the flexibility to give an ablative dose to tumor but allow for differing regimens to spare critical normal tissues depending on tumor location.

Any of the following regimens are considered ablative, acceptable, and are biologically equivalent to 60Gy EQD2:

- Single fraction: 16 Gy total at 16 Gy per fraction (SBRT)
- Three fractions: 24 Gy total at 8 Gy per fraction (SBRT)
- Five fractions: 30 Gy total at 6 Gy per fraction (SBRT). When using five fractions, can reduce to 25 Gy total at 5 Gy per fraction (SBRT) or to a minimum of 20 Gy total at 4 Gy per fraction (SBRT), per treating investigator.
- Six fractions: 32.4 Gy total at 5.4Gy per fraction (Hypofractionated)

If any of the fractions need to be further reduced, this can be done in consultation with the medical monitor.

7.1.2.2 Target Localization

This study requires the use of IGRT. NRG Oncology defines IGRT as a computer-assisted process that uses imaging devices that generate a series of coordinates for shifting the patient support system in three orthogonal directions (sometimes including rotational changes) to position the treatment beams relative to target regions. The allowed technologies are as follows: cone-beam CT (CBCT) using either a specially mounted kV imaging head or the MV treatment beam with an opposed electronic imaging panel, dual fixed-position in-room kV imaging systems that are orthogonal or near orthogonal, an in-room standard diagnostic CT scanner that is geometrically linked to the treatment unit, and the tomotherapy approach.

Simple portal imaging approaches that do not use computer assistance are not considered to be suitable for this study.

When the treatment equipment is not equipped with any device that allows direct visualization of anatomical structures using the treatment beam, the recommendations of AAPM Task Group Report 142 for testing the coincidence of the imaging and treatment reference points must be implemented. For example, verification of treatment and imaging isocenter coincidence must be performed routinely for the CyberKnife, Tomotherapy units as well as any BrainLab equipment that does not include an electronic portal imaging device (EPID) that intercepts the treatment beam.

7.1.2.3 Target Volume Definition

Non-Spinal Osseous Sites: GTV= gross tumor apparent on CT or MRI, or PET/CT imaging. CTV= GTV. PTV will be uniform expansion of 3 to 5 mm.

Spinal Osseous Sites: GTV= gross tumor apparent on CT or MRI, or PET/CT imaging. The GTV will include 1 of the following:

- (a)** The vertebral body only **OR**
- (b)** The vertebral body and pedicle **OR**
- (c)** Posterior elements only

CTV= GTV. PTV will be as per RTOG 0631.

[figure not shown]

Figure 2: Diagram of Spine Metastasis and Target Volume

7.1.2.4 Planning Techniques

General Considerations: A variety of planning techniques can be used to deliver SBRT for each metastasis. General guidelines include the following:

- Multiple coplanar or non-coplanar beam arrangements are acceptable.
- Typically 7 to 13 static radiation beams with equal weighting are used. It is recommended that at least 10 beams be used when possible.
- A minimum field dimension of 3 cm should be observed treating small metastases.
- Dynamic conformal arcs are acceptable. It is recommended that arcs span at least 340 degrees.
- For non-IMRT or dose painting techniques, the conformal field aperture size and shape should correspond nearly identically to the projection of the PTV along a beam's eye view (i.e., no additional "margin" for dose buildup at the edges of the blocks or MLC jaws beyond the PTV). The only exception will be when observing the minimum field dimension of 3 cm when treating small lesions.
- The prescription isodose line covering 95% the PTV will generally be 80-90% but may range from 60-90% where the maximum dose is 100%. As a result, a "hotspot" will exist within the PTV that is equal to the prescription dose divided by the prescription isodose line (i.e., $45\text{Gy}/0.6 = 75\text{Gy}$ when 45Gy is prescribed to the 60% isodose).
- Doses higher than the prescription isodose (i.e., hotspots) should be manipulated to occur within the target.

Dose calculations: All dose distributions shall include corrections for tissue heterogeneities. **Normalization:** The treatment plan should be initially normalized such that 100% corresponds to the maximum dose within the PTV

(MAXPTV). While this point will typically correspond to the PTV center of mass, it can be located elsewhere within the PTV.

1. **Prescription Isodose Surface Coverage:** The prescription isodose surface will be chosen such that 95% of the target volume (PTV) is conformally covered by the prescription isodose surface. Doses less than 95% of the prescription dose are restricted to the outside edges of the PTV. The prescription isodose surface selected MUST be $\geq 60\%$ and $\leq 90\%$ of the dose maximum within the PTV (MAXPTV). The MAXPTV corresponds to the normalization point (100%) of the plan as noted above.

2. **Target Dose Heterogeneity:** Rather than prioritizing target dose homogeneity, SBRT treatment planning prioritizes adequate minimum target coverage and rapid dose fall-off gradients outside of the target. Hot spots within targets are generally accepted without consequence since targets are mostly tumor. The only exception is when the hotspot within the PTV also intersects an OAR.

3. **Critical Organ Doses:** Respect all critical organ dose volume limits as described by either: The report of AAPM Task Group 101, the NRG BR-001 protocol, or the RTOG 0631 treatment protocol.

4. **High-Dose Spillage:**

- a. **Location:** Any dose $> 105\%$ of the prescription dose should occur within the PTV and not within the normal tissues outside the PTV.
- b. **Volume:** Acceptable isodose distributions should be as conformal as possible. To this end the ratio of prescription isodose volume to PTV should be as small as possible.
 - i. The ratio of the prescription isodose volume to the PTV volume should be < 1.2 . Acceptable variations include a ratio of 1.2 to 1.5. Ratios above 1.5 will be considered unacceptable variations. The prescription line for each lesion will be contoured for calculation of this ratio. The prescription line will be labelled as V_{5000} with the 5000 changing to reflect the prescription dose in cGy.
 - ii. Guidelines for the ratio of the 50% prescription isodose volume to the PTV volume (R50%) and for the maximum dose at 2cm (D2cm) from the PTV are given in Table 7.1.2.4. Because it may become more difficult to restrict the 50% isodose volume when dose is summed from treatment of multiple metastases, this ratio should be evaluated for dose calculated for a single metastasis (i.e., not for composite dose). This is acceptable as long as normal tissue constraints are met.
 - iii. Elliptically shaped metastases as well as extremity metastases may not meet these guidelines. This is acceptable as long as normal tissue constraints are respected.
 - iv. These criteria will not be required in treating very small tumors (< 2.5 cm axial GTV dimension or < 1.5 cm craniocaudal GTV dimension) in which the required minimum field size of 3 cm results in the inability to meet a conformity ratio of 1.5.

Table 7.1.2.4

PTV Volume (cc)	Ratio of 50% Prescription Isodose Volume to PTV Volume, R50%	Maximum Dose at 2cm (D2cm) from PTV in any direction as % of Prescribed Dose
1.8	< 7.5	<57.0
3.8	< 6.5	<57.0
7.4	< 6.0	<58.0
13.2	< 5.8	<58.0
22.0	< 5.5	<63.0
34.0	< 5.3	<68.0
50.0	< 5.0	<77.0
70.0	< 4.8	<86.0
95.0	< 4.4	<89.0
126.0	< 4.0	<91.0
163.0	< 3.7	<94.0

NOTE: For values of PTV dimension or volume not specified, linear interpolation between table entries is required.

NOTE: For tumors within 2 cm of the skin, it may be difficult to meet the values for D2cm and R50%. In these cases, these criteria will not be used.

7.2 Radium-223

Radium Ra-223 dichloride will be delivered intravenously at 55 kBq (1.49 mCi)/kg (+/- 10% total dose) for a total of six cycles. 1 cycle= 28 days. The first cycle will commence at study enrollment, then cycles 2 through 6 will commence after the completion of radiotherapies at 4-week intervals.

7.2.1 How Supplied, Stored, Packaged, and Labeled

The alpha-pharmaceutical Radium Ra-223 dichloride is a ready-to-use, sterile, non-pyrogenic, clear, and colorless aqueous solution of Radium Ra-223 dichloride ($^{223}\text{RaCl}_2$) for IV administration. It should not be diluted or mixed with any solutions. Each vial is intended for a single use only. Radium-223 ordering documents are located in Appendix 17.3 Clinical Supply Agreement. Instructions for Huntsman Cancer Institute may be performed using the HCI Ordering and Scheduling Process for Radium.

Radium Ra-223 dichloride is an alpha particle emitter with a physical half-life of 11.4 days. The product is isotonic and has a pH of 6.0 to 8.0.

The radioactive concentration at the reference date is 1,100 kBq/mL. The product has a pre-calibration of 14 days. When administered on a day other than the

reference day, the volume should be corrected according to the physical decay table accompanying each shipment.

Decay Correction Factor Table

Days from reference date	Decay Factor	Days from reference date	Decay Factor
-14	2.296	0	0.982
-13	2.161	1	0.925
-12	2.034	2	0.870
-11	1.914	3	0.819
-10	1.802	4	0.771
-9	1.696	5	0.725
-8	1.596	6	0.683
-7	1.502	7	0.643
-6	1.414	8	0.605
-5	1.330	9	0.569
-4	1.252	10	0.536
-3	1.178	11	0.504
-2	1.109	12	0.475
-1	1.044	13	0.447
		14	0.420

Radium Ra-223 dichloride, is manufactured by Bayer Healthcare LLC contract manufacturer Algeta's Institute for Energy Technology, Isotope laboratories, Kjeller, Norway. The product is produced according to Good Manufacturing Practice (GMP). The product will be delivered in a glass vial, ready-to-use with a certified activity. Radium Ra-223 dichloride is shipped in a lead container and Type A radioactive package according to international transportation guidelines for radioactive materials.

The volume per vial is 6 mL, corresponding to 6.6 MBq at the reference day. Radium Ra-223 dichloride has a shelf life of 28 days from production day, when stored at ambient temperature. The shelf life has been demonstrated for temperatures from cold storage (2-8°C) up to 40°C. In addition, it has been shown that the product quality is not jeopardized upon freezing.

All study drugs will be labeled according to the requirements of local law and legislation. For all study drugs, a system of numbering in accordance with all requirements of GMP will be used, ensuring that each dose of study drug can be traced back to the respective bulkware of the ingredients.

7.2.2 General warning RA-223

Radium-223 dichloride should be received, used, and administered only by authorized persons in designated clinical settings. The receipt, storage, use, transfer, and disposal Radium-223 dichloride are subject to the regulations and/or appropriate licenses of the competent official organization. Radium-223 dichloride should be handled by the user in a manner that satisfies both radiation

safety and pharmaceutical quality requirements. Appropriate aseptic precautions should be taken.

7.2.3 Radiation protection RA-223

The administration of Radium Ra-223 dichloride is associated with potential risks for other persons (e.g., medical staff, care givers, and members of the patient's family) from radiation or contamination from spills of body fluids such as urine, feces, or vomit. Therefore, radiation protection precautions must be taken in accordance with national and local regulations.

For drug handling

Follow the normal working procedures for the handling of radiopharmaceuticals and use universal precautions for handling and administration such as gloves and barrier gowns when handling blood and bodily fluids to avoid contamination. In case of contact with skin or eyes, the affected area should be flushed immediately with water. In the event of spillage of Radium Ra-223 dichloride, the local radiation safety officer should be contacted immediately to initiate the necessary measurements and required procedures to decontaminate the area. A complexing agent such as 0.01 M ethylene-diaminetetraacetic acid (EDTA) solution is recommended to remove contamination.

For patient care

Whenever possible, patients should use a toilet and the toilet should be flushed several times after each use. When handling bodily fluids, simply wearing gloves and hand washing will protect caregivers. Clothing soiled with Radium Ra-223 dichloride or patient fecal matter or urine should be washed promptly and separately from other clothing.

Radium-223 is primarily an alpha emitter, with a 95.3% fraction of energy emitted as alpha-particles. The fraction emitted as beta-particles is 3.6%, and the fraction emitted as gamma-radiation is 1.1%. The external radiation exposure associated with handling of patient doses is considerably lower in comparison to other radiopharmaceuticals for therapeutic purposes as the administered radioactivity will usually be below (8.8MBq(0.238mCi)). In keeping with the **As Low As Reasonably Achievable (ALARA)** principle, for minimization of radiation exposure, it is recommended to minimize the time spent in radiation areas, to maximize the distance to radiation sources, and to use adequate shielding. Any unused product or materials used in connection with the preparation or administration are to be treated as radioactive waste and should be disposed of in accordance with local regulations. The gamma radiation associated with the decay of Radium-223 and its daughters allows for the radioactivity measurement of Radium Ra-223 dichloride and the detection of contamination with standard instruments.

Dose calibration

Radium Ra-223 dichloride can be measured in a normal dose calibrator instrument. A vial of Radium Ra-223 dichloride for technical use will be sent to the study center.

Different clinical study centers possess dose calibrators from various suppliers; thus, the isotope calibration factor may differ from center to center. Consequently, each center must perform the Radium Ra-223 dichloride dial setting on their relevant dose calibrator(s) the amount of Radium Ra-223 dichloride in the vial will be stated on the label. Instructions for the dial setting, including the calibration log form, will be enclosed with the dispatch of the calibration sample.

7.2.4 Dosimetry

The absorbed radiation dose calculation was performed based on clinical biodistribution data. Calculations of absorbed doses were performed using OLINDA/EXM (Organ Level INternal Dose Assessment/EXponential Modeling), a software based on the Medical Internal Radiation Dose (MIRD) algorithm, which is widely used for established beta and gamma emitting radionuclides. For Radium-223, which is primarily an alpha emitter, additional assumptions were made for the intestine, red marrow and bone/osteogenic cells to provide the best possible absorbed dose calculations for Radium Ra-223 dichloride, considering its observed biodistribution and specific characteristics. For an administered activity of 4.00 MBq (0.109 mCi) ((55kBq (.0015 ciper kg body weight to a 73-kg adult), the calculated absorbed doses to the bone (osteogenic cells) is 4.2050 Gy (420.5 rad) and to the red marrow is 0.5066 Gy (50.66 rad). The calculated absorbed doses to the main excretory organs are 0.0265 Gy (2.65 rad) for the small intestine wall, 0.1180 Gy (11.8 rad) for the upper large intestine wall and 0.1696 Gy (16.96 rad) for the lower large intestine wall.

The calculated absorbed doses to other organs are low, e.g. heart wall (0.0063 Gy, 0.63 rad), lung (0.0003 Gy, 0.03 rad), liver (0.0109 Gy, 1.09 rad), kidneys (0.0117 Gy, 1.17 rad), urinary bladder wall (0.0147 Gy, 1.47 rad), testes (0.0003 Gy, 0.03 rad), and spleen (0.0003 Gy, 0.03 rad).

The hematological adverse drug reactions observed in the clinical studies with Ra-223 are much lower in frequency and severity than what could be expected from the calculated absorbed doses to the red marrow. This may be related to spatial distribution of alpha particle radiation resulting in non-uniform radiation dose to the red marrow.

7.2.5 Dose handling

The Radium Ra-223 dichloride vials must be stored inside their lead container in a secure facility. The study drug should be used within 28 days of production. Radium Ra-223 dichloride is an alpha-pharmaceutical and should be handled by individuals who are qualified by training and experience in the safe handling of radionuclides. One dedicated person and a back-up designee will have responsibility as assigned from the Primary Investigator for handling and storage

of Radium Ra-223 dichloride. All administrations of Radium Ra-223 dichloride are based on the certified activity of Radium Ra-223 dichloride at the calibration date.

7.2.6 Dose calculation

The dosage of Radium Ra-223 dichloride is 55 kBq (1.49 mCi)/kg body weight (as documented in the written directive) (+/- 10% total dose). The patient dose is calculated based on date of injection, a decay correction (DK) factor specific to number of days from reference date applied to correct for physical decay of Radium-223, and patient weight. A table with DK values according to physical decay of the study medication will be provided with every shipment of Radium Ra-223 dichloride. Radium-223 is an alpha particle emitter with a physical $t^{1/2}$ of 11.4 days.

For example: If the radioactive concentration at the reference date is 11,100 kBq/mL then the volume to be administered for the current dose is calculated as follows:

Body weight (kg) X dose (55kBQ/kg body weight)
DK factor X 1100kBq (0.0297 μ Ci)/mL

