Study Duration	3-4 years (accrual at 2 patients per month. Study duration 6 months per patient. 2 year follow up.)
Study Center(s)	This is a single site study conducted at the Huntsman Cancer Institute
Objectives	Primary Objective: Freedom from Androgen Deprivation Therapy (ADT) or other antineoplastic systemic at 15 months. Secondary Objective: QOL assessments, Progression Free Survival, Overall Survival
Number of Subjects	20
Diagnosis and Main Eligibility Criteria	Men with Prostate Cancer and no more than 5 sites of bony metastatic disease without visceral involvement.
Study Product, Dose, Route, Regimen	
 Radium-223 55 kBq (1.49 mCi)/kg (+/- 10% total dose) at study enrollment, and then every 4 weeks following definitive radiation therapy for a total of six Radium-223 infusions. Hypofractionated Radiotherapy to all oligometastatic sites
Duration of administration	6 months of therapy
Reference therapy	Institutional Care Standard (99% of subjects starting Androgen Deprivation Therapy by 15 months)

Statistical Methodology	Assess the proportion of ADT naïve men who progress and require ADT at 15 months.
-------------------------	-----------------------------------------------------------------------------------

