3.1.1 Description

Radium Ra-223 dichloride, an alpha particle-emitting pharmaceutical, is a radiotherapeutic drug. Radium Ra-223 dichloride is supplied as a clear, colorless, isotonic, and sterile solution to be administered intravenously with pH between 6 and 8. Each milliliter of solution contains 1100 kBq Radium-223 dichloride (30 microcurie), corresponding to 0.58 ng radium-223, at the reference date. Radium is present in the solution as a free divalent cation. Each vial contains 6 mL of solution (6,600 kBq (178 microcurie) Radium-223 dichloride at the reference date). The inactive ingredients are 6.3 mg/mL sodium chloride USP (tonicity agent), 7.2 mg/mL sodium citrate USP (for pH adjustment), 0.2 mg/mL hydrochloric acid USP (for pH adjustment), and water for injection USP. The molecular weight of Radium-223 dichloride, $^{223}\text{RaCl}_2$, is 293.9 g/mol. Radium-223 has a half-life of 11.4 days. The specific activity of Radium-223 is 1.9 MBq (51.4 microcurie)/ng. The six-stage-decay of Radium-223 to stable lead-207 occurs via short-lived daughters, and is accompanied predominantly by alpha emissions. There are also beta and gamma emissions with different energies and emission probabilities. The fraction of energy emitted from Radium-223 and its daughters as alpha-particles is 95.3% (energy range of 5 - 7.5 MeV). The fraction emitted as beta-particles is 3.6% (average energies are 0.445 MeV and 0.492 MeV), and the fraction emitted as gamma-radiation is 1.1% (energy range of 0.01 - 1.27 MeV).

NIST Standardization

The quantification of Radium-223 radioactivity is based on the primary standardization performed by the US NIST. National Institute of Standards and Technology prepares the standard reference material (SRM) using an official dial setting (primary standardization) as published (as provided in the Investigator Brochure). The NIST SRM is used to calibrate the instruments in production and

quality control for both the drug substance and drug product. Additionally, the NIST SRM is used to prepare the NIST traceable Ra-223 reference materials which are then sent to the end users (e.g., nuclear medicine laboratory physicians or technicians) for dial-setting of their dose calibrators, to allow verification of the patient dose.

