In 2014, NIST performed a re-assessment of the primary standardization based on preliminary information suggesting a potential discrepancy of approximately 8-10% between the published NIST primary standardization (as provided in the Investigator Brochure) and results obtained by other national metrology institutes (United Kingdom, Germany, Japan). After completion of the re-assessment, NIST reported their findings (as provided in the Investigator Brochure) and had issued a revised NIST SRM in 2015. The discrepancy in the NIST standardization was determined to be -9.5% between activity values obtained using the old reference standard relative to the new primary standardization. Consequently the current numerical values need to be corrected by approx. + 10.5%.

The current NIST standard for Radium-223 dichloride remained in effect until 4/25/16. As of that date the FDA approved the regulatory variation submitted for Radium-223. The change in the numerical description of the patient's dose, product strength and labeled vial activity does not impact the safety or efficacy of Radium-223. The change in the NIST Radium-223 standard has no impact on subjects; dose subjects are receiving, and will continue to receive. Subjects will receive the same actual dose and volume that was studied in Study 15245 (BC1-06 dosimetry study) and is associated with the proven safety and efficacy of Radium-223 dichloride, though the stated nominal radiation dose received is being updated to reflect the new standard. The current dose regimen of Radium-223 is 55 kBq (1.49 microcurie) per kg body weight.

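### The treatment sections pair 55 kBq/kg with a curie figure about 1000 times larger, and the dose-calculation example opens with a concentration about 10 times the one in its own formula

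*Combined protocol and SAP*

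**What the plan says.** The per-kilogram dose appears in four places, always with the same kBq figure but with two different curie figures:

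- Study Summary: "Radium-223 55 kBq (1.49 mCi)/kg (+/- 10% total dose) at study enrollment".
- Section 7.2: "delivered intravenously at 55 kBq (1.49 mCi)/kg (+/- 10% total dose) for a total of six cycles".
- Section 7.2.6: "The dosage of Radium Ra-223 dichloride is 55 kBq (1.49 mCi)/kg body weight", tied there to the written directive and to a +/-10% tolerance on the total dose.
- Section 3.1.1, NIST Standardization: "The current dose regimen of Radium-223 is 55 kBq (1.49 microcurie) per kg body weight".

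Section 7.2.6 then gives a worked example for the volume to inject. It begins "If the radioactive concentration at the reference date is 11,100 kBq/mL", but the denominator printed below it is the decay factor times 1100 kBq/mL, with 0.0297 microcurie in brackets. Section 7.2.1 says "The radioactive concentration at the reference date is 1,100 kBq/mL" and gives a 6 mL vial as 6.6 MBq. Section 3.1.1 gives 1100 kBq per mL as 30 microcurie.

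Section 8.1.1 does not permit the dose level to be adjusted.

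**The concern.** A dose written in two units should describe one quantity. Here three of the four statements join two figures that differ by three orders of magnitude, and the fourth uses the other unit. The worked example has two further mismatches: its opening concentration is not the one in its formula, and the formula's bracketed curie value does not equal the kBq value beside it.

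Sections 7.2 and 7.2.6 are the operative dosing text. If a reader writes the directive in millicuries from these sections, or puts the example's stated concentration into the formula, the result contradicts the rest of the protocol by far more than the +/-10% allowed. Even if nobody does so, compliance with a +/-10% tolerance cannot be audited in curies when the curie value is inconsistent.

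**Working it through.** **Conversion used.** 1 microcurie = 37 kBq and 1 mCi = 37,000 kBq, by definition of the curie. The protocol's other pairs imply the same factor within rounding:

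| Place | Pair given | kBq per microcurie |
|---|---|---|
| 3.1.1, per mL | 1100 kBq = 30 microcurie | 36.7 |
| 3.1.1, per vial | 6,600 kBq = 178 microcurie | 37.1 |
| 3.1.1, current dose | 55 kBq = 1.49 microcurie | 36.9 |
| 7.2.3, usual upper activity | 8.8 MBq = 0.238 mCi | 37.0 |
| 7.2.4, 73 kg adult | 4.00 MBq = 0.109 mCi | 36.7 |
| Summary, 7.2, 7.2.6 dose | 55 kBq = 1.49 mCi | 0.0369 |
| 7.2.6 formula | 1100 kBq = 0.0297 microcurie | 37,037 |

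The last two rows are out by about 1000, in opposite directions.

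**1. Dose statement.**

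- 55 / 37 = 1.486 microcurie = 0.001486 mCi.
- 1.49 x 37,000 = 55,130 kBq.
- 55,130 / 55 = 1,002.

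For a 73 kg adult, 73 x 55 = 4,015 kBq = 0.1085 mCi, which reproduces the 4.00 MBq (0.109 mCi) of Section 7.2.4. The millicurie figure read literally gives 73 x 1.49 = 108.8 mCi, or 4,024 MBq, about 998 times that 0.109 mCi.

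**2. Example concentration.**

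- 11,100 / 1,100 = 10.09.
- A 6 mL vial at 11,100 kBq/mL would hold 66.6 MBq; Section 7.2.1 says 6.6 MBq.

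The formula is volume = weight x 55 / (decay factor x concentration). Inputs: 73 kg (Section 7.2.4) and decay factor 0.982 (day 0 in the 7.2.1 table).

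- At 1,100 kBq/mL: 4,015 / (0.982 x 1,100) = 3.72 mL.
- At 11,100 kBq/mL: 4,015 / (0.982 x 11,100) = 0.37 mL.

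If the smaller volume were drawn from a vial at 1,100 kBq/mL, it would carry 1,100 / 11,100 = 9.9% of the 4,015 kBq, a shortfall of about 90%.

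**3. Bracketed conversion in the formula.** 1100 / 37 = 29.7 microcurie = 0.0297 mCi. The printed value is 0.0297 microcurie, 1000-fold below its kBq partner and in conflict with the 30 microcurie of Section 3.1.1.

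**The case against.** The strongest reply is that the path from dose to volume never uses the inconsistent curie figures. Every statement of this trial's dose gives 55 kBq/kg. The printed formula runs in kBq and divides by 1100, so someone who simply follows it gets a volume consistent with Sections 3.1.1 and 7.2.1. The 0.37 mL result requires substituting a number that the formula does not contain.

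A literal 1.49 mCi/kg could hardly go unnoticed. At 73 kg it would need about 610 vials (4,024 / 6.6) and would be about 457 times the 8.8 MBq below which Section 7.2.3 says administered activity usually lies. There are other controls: certified activity, a decay table with each shipment, dose-calibrator verification and trained handlers. Section 7.2.1 also points to an ordering appendix (17.3) and an institutional ordering process. That appendix was not in the text available to me, so I cannot say which figures staff use when ordering.

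All of this stands as an argument about likelihood: a 1000-fold misdose is implausible. It does not remove the contradiction from the text that defines the dose, and relying on staff to notice and ignore wrong figures is a weak control for an injected alpha emitter.

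A fault in reading the PDF is also possible in principle, and the symbols should be checked against the PDF. It is a poor explanation. The millicurie pairing is identical in three separate places, Section 7.2.6 shows both the millicurie unit and a micro sign, and the mismatch in the formula sits at the micro sign itself. I have not relied on the visibly garbled curie text in Section 7.2.4.

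**Conclusion.** The point holds and should be fixed before anyone relies further on these sections. The Study Summary and Sections 7.2 and 7.2.6 equate two activities that differ about 1000-fold, and they conflict with Section 3.1.1. The example in 7.2.6 conflicts about 10-fold with its own formula, and that formula carries a further 1000-fold unit mismatch. The unit findings rest only on the definition of the curie and the printed figures. The illustrative volumes also assume a 73 kg patient dosed on the reference day, but the 10-fold ratio does not depend on weight or day.

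Harm is conditional on someone using an inconsistent figure. I take no view on which dose or concentration is the intended one. Endpoint, alpha, power and sample size are not touched.

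**What to change.** The sponsor should confirm the intended dose and product concentration, then reconcile:

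- the dose statements in the Study Summary and Sections 7.2, 7.2.6 and 3.1.1, so that each carries the same kBq figure and a curie figure that matches it by arithmetic;
- the opening concentration of the 7.2.6 example, the concentration in its formula, and Sections 7.2.1 and 3.1.1;
- the bracketed curie value in the 7.2.6 formula with the per-mL pair in Section 3.1.1.

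The same figures should be checked in Appendix 17.3 and in any local worksheet built from Section 7.2.6. The pharmacy and nuclear medicine staff who prepare doses should be told of the correction directly.

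The cost is a short amendment to a few dose statements and one worked example, with no effect on the data, the analysis or the sample size.
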